Evidence-based implementation strategies. Evidence-based implementation strategies help facilitate the translation of research to practice through mitigating barriers to quality implementation of effective interventions. 14 Implementation strategies are needed to realize the public health benefits of EBPs. 35 Replicating Effective Programs (REP) is an implementation strategy focused on maximizing flexibility and fidelity in EBP delivery.²³ Unlike other implementation strategies (e.g., evidence-based quality improvement, NIATx), 36,37 REP was developed for community-based settings to implement EBPs and has been used with prevention-focused interventions. REP, based on the CDC's research-to-practice framework, 38 is guided by Social Learning³⁹ and Diffusion of Innovations Theories.⁴⁰ Standard REP includes three primary componentsprogram packaging, provider training, and facilitation (Table 3). Standard REP is a low intensity, minimal cost intervention that has improved uptake of brief HIV-focused interventions. 41 Researchers have also developed enhanced REP for more complex clinical behavioral interventions, which includes added customization for program packaging and training, and active engagement of internal and external facilitator.⁴² Information about organizational context, providers and the intervention are essential to customizing REP for optimal programorganization fit. Researchers have found enhanced program fidelity among clinical sites using enhanced versus standard REP.⁴³ REP and enhanced REP, however, have not been tested in school settings and very little research has been done to investigate the effects of either REP on implementation and behavioral outcomes in school settings. Although improved outcomes with enhanced REP are promising, the added costs can be substantial.⁴³ Thus, economic evaluation is vital to assess the costs and benefits of different strategies.

 Table 3: Replicating Effective Programs (REP) Components (adapted from Kilbourne et al, 2015)

	Standard REP	Enhanced REP
Package	Intervention manual development	Intervention manuals customized to sites using data from organization needs assessment on population and setting resources
Training	Standard training	Customized training based on input from package step above

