Facilitation	As needed technical assistance; Monitor intervention uptake via	External facilitation components : Works with IF and providers to review potential barriers and set goals; Technical assistance: EF gives specific implementation guidance and facilitates information sharing and long-term plans for sustainability
	observation, qualitative and quantitative data	Internal facilitation components : Regular meetings with EF, providers to set goals, align intervention with organization, advocate for implementation to leadership

Economic evaluation of implementation. The goal of implementation research is to determine the best strategies to improve EBP delivery in community settings. Most economic evaluation in implementation, however, has focused on the costs of interventions and *not* the costs of implementation strategies required to deploy and sustain interventions in community settings. 13 Understanding the resources needed to achieve desired behavioral outcomes (e.g., reduced ATOD use) is essential to implementing EBPs. 44 Because economic factors related to implementation influence the program delivery, 12,13,15 economic evaluation can inform implementation strategies. 45,46 Systematic examination of outcomes related to implementation strategies, and the costs of achieving them, is essential for integrating EBPs in real-world settings. 13 Organizations benefit from evidence that supports (or refutes) investment in specific implementation strategies as an efficient use of resources and can help prioritize implementation efforts. The Cost of Implementing New Strategies (COINS) provides a useful framework for evaluating implementation costs.⁴⁴ COINS aids in identifying a range of costs across multiple phases of implementation (e.g., pre-implementation, implementation, and sustainability) and is congruent with REP phases (see Table 7). 23,44 Many types of economic evaluation exist, but one well suited to implementation science is cost-effectiveness. Costeffectiveness assesses whether incremental benefits of one strategy versus another are sufficient to justify additional costs and has been used to support selective EBPs for youth in clinical settings^{47,38} Costeffectiveness data can help inform decisions about resource allocation for program selection and implementation.⁴⁵ Economic analysis of implementation strategies, however, is understudied.

Significance of the Expected Research Contribution

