Aim 3: MMH REP pilot: building on the skills developed in Aim 1 and Training Goals 1-3, I will conduct a prospective implementation pilot of the MMH in the GISD. REP is well suited for implementing MMH because it includes a curriculum manual and teacher training processes. The overall purpose of this pilot is to assess the appropriateness, feasibility, and acceptability of using REP for MMH, a universal ATOD prevention program. 62 I will create a customized package for delivering MMH using standard and enhanced REP. Informed by data from Aim 1, I will investigate the effectiveness of standard and enhanced REP on implementation and behavioral outcomes. Sample and setting. We will study high schools from Genesee County, MI. Like other communities facing declining populations and economic challenges, the county has had higher unemployment levels compared to state and national averages for over a decade, 66 and youth report higher rates of ATOD use compared to state averages (Table 6). This pilot study will include 8 schools from the Genesee Intermediate School District (GISD), as informed by other implementation pilot studies⁶² and study resource limitations. GISD includes 21 school districts and 25 public high schools. In collaboration with GISD partners, we will identify high schools using MMH that fail to meet MI DHHS standards for implementation (75% or less of the curriculum) to contact regarding participation. We will select schools using data from our MMH implementation study that have comparable student demographics (e.g., % free/reduced lunch). Procedures. We will recruit schools in collaboration with GISD leadership. Identified schools will be randomized to either standard REP or enhanced REP (see Table 3). The standard REP condition will receive a customized MMH manual (adapted from the current manual) based on results from Aim 2 to meet the needs of the context and providers; this may include creating on online manual. Standard REP will also include customized training based on Aim 2 (e.g., adapting content to new substances or substance forms, updated teacher resources) and brief, as needed technical assistance. Enhanced REP will also include internal and external facilitators with specific expertise in health education and implementation with weekly teacher contact to provide specific guidance for overcoming MMH delivery barriers. Enhanced REP will also include additional training and packaging customization (e.g., supplemental ATOD resources). The study team will meet with teachers and parents at participating schools to share study information. Teachers will complete a survey on MMH implementation and using Enhanced REP to deliver MMH post-intervention. We will also conduct qualitative interviews of teachers in participating schools to obtain in-depth information about using MMH delivery with REP. Students receiving the MMH at participating schools will be eligible for student-level surveys. Students will be recruited in participating schools in conjunction with GISD partners. Following parental consent and participant assent, students will complete a self-administered questionnaire through a secure, online survey about ATOD and related behaviors. As MMH is integrated as part of the school curriculum, students will complete the initial survey during their 9th or 10th grade health class prior to MMH delivery and 3 months postdelivery. Students who do not consent will receive an alternate activity. I expect 300 students to participate based on a 60% response rate. 67 Students will receive \$10 for the surveys.

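### Does the mismatch between Table 3 and the Aim 3 procedures on standard REP training leave the pilot's comparator undefined?

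*Combined protocol and SAP*

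**What the plan says.** The Aim 3 procedures set up the comparison and refer back to the background section: "Identified schools will be randomized to either standard REP or enhanced REP (see Table 3").

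The next sentences describe the standard arm. On the manual: "The standard REP condition will receive a customized MMH manual (adapted from the current manual) based on results from Aim 2". On training: "Standard REP will also include customized training based on Aim 2", with updated substance content and teacher resources as examples. Technical assistance is brief and given on request. Enhanced REP then adds internal and external facilitators in weekly contact with teachers, and further tailoring of training and package.

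Table 3 stands in the Significance section, under evidence-based implementation strategies. Its training row reads "Standard training" for standard REP and "Customized training based on input from package step above" for enhanced REP. Its package row gives standard REP the development of a manual and gives enhanced REP "Intervention manuals customized to sites using data from organization needs assessment on population and setting resources". Its facilitation row starts, for standard REP, with "As needed technical assistance". The paragraph above the table describes enhanced REP as a version "which includes added customization for program packaging and training".

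**The concern.** In Table 3, tailoring is what separates the two arms on training: one has it and the other does not. In the Aim 3 text both arms have it and the enhanced arm has more. Because the Aim 3 text cites the table without noting any departure, a reader could fairly conclude that the comparator has two definitions.

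What the comparator receives determines what the pilot estimates. Under a literal reading of the table, the effect of condition would include tailored versus untailored training. Under the Aim 3 text it is facilitation plus extra tailoring over an REP that is already tailored, which is narrower on training. The same question reaches the Aim 3b cost difference: is training customisation shared between the arms, or charged to enhanced REP alone? Table 7 lists 23 activities, 3 of which name training, and has no column for arm.

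**Working it through.** The plan gives no figure to reproduce here, so the check sets the two sources side by side.

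| Component | Table 3, standard | Table 3, enhanced | Aim 3 text, standard | Aim 3 text, enhanced |
|---|---|---|---|---|
| Package | Manual developed | Manual tailored to each site from a needs assessment | Manual tailored from Aim 2 | Same base, plus more tailoring |
| Training | Labelled standard | Tailored from the package step | Tailored from Aim 2 | Same base, plus more tailoring |
| Facilitation | Assistance as needed | Internal and external facilitators | Assistance as needed | Internal and external facilitators |

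(The enhanced entries for the Aim 3 text assume that enhanced REP builds on the standard arm, as its wording about adding suggests.)

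1. **Facilitation.** The two sources agree.

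2. **Package.** The table's enhanced manual is tailored to sites. The standard manual in the Aim 3 text is tailored from Aim 2, which rests on a survey of Michigan health teachers (20 already in hand and 200 expected, so 220) and on interviews. That is not a needs assessment of each pilot school. The two kinds of tailoring differ, so the conflict is partial at most.

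3. **Training.** The same distinction applies. The table's enhanced training takes its input from the package step, which is the site needs assessment. The standard arm's training in the Aim 3 text is a content update drawn from Aim 2. One updated training given to every standard-arm school can still be standard in the table's sense, because it is not tailored to the site. This row is also a partial conflict at most.

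4. **Other text.** The opening of Aim 3 plans a tailored MMH package for use with both forms of REP. Aim 2 says its results will shape the design of REP for MMH, and its expected outcomes say they will inform REP in the pilot. None of these limits Aim 2 tailoring to the enhanced arm. The background paragraph speaks of customisation that is added in enhanced REP, which fits a common base with a further layer.

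5. **Cost.** Let T be the cost of the common training tailoring, X the enhanced arm's additional tailoring and F facilitation. Under the Aim 3 text, with other shared work cancelling,

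   Cost(E-REP) − Cost(REP) = (T + X + F) − T = X + F.

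   Table 3 lists a single tailored-training item for enhanced REP. Call its cost C. Setting the package aside, the table's difference is C + F, and the gap between the readings is (C + F) − (X + F) = C − X. This is zero if the table's site-level tailoring is the additional layer that the Aim 3 text describes. A gap of T arises only if the Aim 3 text's extra layer X is carried into the table's scenario on top of T (C = T + X), and the table does not list such a layer. The documents give no value for T, X, C or F.

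6. **Use of the results.** Aim 3b records staff and partner time and non-labour costs for REP activities, so costs should follow what is done in each arm. The expected outcomes in Aims 3a and 3b compare enhanced with standard REP, and none claims a contrast with untailored training. Aim 3a carries outcome variances forward to plan the larger study, and nothing in the documents shows that the training label changes them.

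**The case for a change.** The strongest case for acting is that the Aim 3 text names Table 3 as its reference, notes no departure, and gives the standard arm something that the table shows only for the other arm. No sentence states that standard training in the table covers training tailored from Aim 2. The background phrase about added customisation describes REP in general, and the mid-year progress note mentions a tailored training without naming an arm. Table 7 does not assign activities to arms, and the planned sensitivity analyses vary input values, not which arm bears a cost. The document is dated 10/20/2020 and the pilot was planned for early 2021, so a wording edit would have been cheap and in time.

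Part of this stands. The wording mismatch is real, and someone reading Table 3 alone would think the arms differ by the presence or absence of tailored training. What does not stand is the step from there to an undefined comparator. A parenthetical reference to a general table does not readily override the trial-specific sentences that follow it. The fear that delivery, costing and reporting would each use a different comparator is conjecture, given that the procedures say what each arm gets and the cost data come from logged activity.

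**Conclusion.** This is a clerical mismatch of partial extent, and no change to the plan is needed. Of the three rows of Table 3, one agrees with the Aim 3 text, and two differ only in whether the standard arm is credited with Aim 2 tailoring. No numerical size can be given, because the documents contain no cost or effect for training tailoring.

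Following the Aim 3 procedures as written gives a sound randomised contrast across the 8 schools: facilitation plus additional tailoring of training and package, over an REP already informed by Aim 2. The models, the outcomes and the cost-effectiveness ratio stay as they are. A footnote to the table would tidy the text but change no result.

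The conclusion rests on three assumptions: that schools receive what the Aim 3 procedures describe, that costs are logged by arm as activities occur, and that the report describes each arm by what it received. If the standard arm were in fact given untailored training, the contrast would be wider on that component, and an accurate description of the arms would show it.

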used (e.g., active learning) and engagement in specific MMH activities (e.g., four corners discussion) as detailed in the curriculum. 12,68 We will create teacher checklists of MMH lesson components and create a composite adherence score based on the checklist. Acceptability, appropriateness, and feasibility (REP): We will use Weiner et al.'s^{53,56} measures to assess acceptability, appropriateness, and feasibility. Each construct has 4 items (e.g., REP is appealing, REP seems suitable), from 1: Strongly disagree to 5: Strongly agree. ATOD and associated outcomes (behavioral outcomes): We will use items from CDC's Youth Risk Behavior Survey, ⁶⁹ that includes measures for substance use including tobacco, marijuana, alcohol, and other drugs, and associated consequences (e.g., injury, DUI). We will also assess MMH-specific constructs using an adapted survey of MMH from O'Neill et al.; this includes drug refusal skills (e.g., identifying proper responses to peers when offered drugs) and self-management skills (e.g., identifying appropriate ways to express anger or frustration).²⁷ Implementation factors and outcomes (qualitative data): We will use the CFIR interview guide⁵⁷ to guide qualitative investigation of using REP to deliver MMH; this will focus on factors identified in Table 5, and adapted based on results from Aim 1. In addition, we will ask for in-depth feedback on acceptability, feasibility, and appropriateness from teachers regarding the delivery of MMH using REP. The questions are guided by the constructs listed in Table 4. Data analytic approach. Implementation outcomes: We will assess adherence using the composite adherence score. We will evaluate appropriateness. acceptability and feasibility using data from the teacher survey and interviews. Qualitative data will be analyzed as described in Aim 1 and we will triangulate the findings using descriptive data from the Weiner et al. measures.⁵³ Behavioral intervention effectiveness: Given the sample size associated with this pilot study, we will focus on estimating intervention effects, variance of the treatment effect, and directions of associations with outcomes of interest as opposed to statistical significance. ⁷⁰ We will use generalized linear models to investigate the effects of implementation condition on ATOD use and related consequences at 3 months postintervention, controlling for demographics and baseline functioning, and accounting for clustering by school, We will test the overall main effect of implementation condition on outcomes and investigate mean values of outcomes (e.g., substance use) by condition.⁷¹ We will also investigate ATOD use by sex to determine if the intervention condition had differential effects. Finally, we will use variance estimates of outcomes to inform sample size calculation for a larger, multi-site effectiveness study that will be the focus of a future R01 proposal. Expected outcome: We expect that enhanced REP will increase adherence to the MMH curriculum compared to standard REP and teachers will report REP is feasible, acceptable, and appropriate to guide MMH delivery. We also expect that students in schools with enhanced REP will report less ATOD use than those with standard REP.

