
Aim 3b: Procedures. Guided by Costs of Implementing New Strategies (COINS), we will monitor the activities listed in Table 7 to estimate implementation strategy costs. The study team will track time for labor costs-most of the resource/costs. This will include tracking time in study team activities as well as time logs for community partners to track REP activities. The study team will also track and compile all non-labor costs. **Measures.**Costs: Implementation cost measures are guided by COINS and include indirect and non-labor costs. We will measure implementation costs using available cost data from the school district, summary data from previous empirical studies on implementation costs, and routinely available cost data using market prices. 45

Table 7: Intervention costs informed by Costs of Implementing New Strategies (COINS)

Phases	Description	Activities	Resource/cost type
Pre-	-		
implementation	Identify barriers	Stakeholder meetings	RF, PM/ labor costs
		Survey	Secondary data, PM, RF/labor cost
		Interviews	Secondary data, PM, RF/labor cost
	Draft package	Identify adaptations	RF, CP/ labor costs
		Identify core elements	RF, CP/ labor costs
		Program adaptations: online	P/ labor costs
			domain costs/nonlabor
		Program adaptations: manual	PM, RA/ labor costs
	Pilot test package	refinement	RF, RA, PM/ labor costs
	Orientation	identify schools	RF, PM, CP/ labor costs
		Logistics of delivery	RF, PM/ labor costs
		Refine training	RF, CP/ labor costs

		Identify EF IF	CP/ labor costs
	Training	Staff training: intervention	RF. CP/ labor costs
			travel costs, RF/nonlabor
			training compensation/nonlabor
			space/nonlabor
Implementation			hosting/nonlabor
		Disseminate package	PM/labor costs
	Technical assistance	Internal facilitation	CP/ labor costs
		External facilitation	PM/labor costs
	Evaluation	Interviews	RF, RA/labor costs
			remuneration/nonlabor
		Survey	RF, RA/labor costs
			remuneration/nonlabor
	Refinement	Analyze data	Secondary data, PM, RF/labor costs
		training, package refinement	PM, RF, CP/labor costs
	Organizational		
Sustainability	changes	Recommendations for REP	PM, RF, CP/labor costs
		Reproduce package	CP/ labor costs
		Continue to refine	CP, RF/labor costs

PM: project manager; RA: research assistant; RF: research faculty, CP: community partner, P: programmer Table adapted from Saldana et al¹⁴

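### Does the adherence score favor one arm because the checklist is not tied to a single MMH manual version?

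*Combined protocol and SAP*

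**What the plan says.** Under Aim 3a, Measures, adherence is reported by teachers and covers procedures used and "engagement in specific MMH activities (e.g., four corners discussion) as detailed in the curriculum". The instrument is still to be made: "We will create teacher checklists of MMH lesson components and create a composite adherence score based on the checklist". The analysis paragraph adds only that the composite will be used. The Expected outcome paragraph compares arms: "We expect that enhanced REP will increase adherence to the MMH curriculum compared to standard REP".

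Under Aim 3, Procedures, the arms are introduced by "Identified schools will be randomized to either standard REP or enhanced REP (see Table 3"). Standard REP is then described: "The standard REP condition will receive a customized MMH manual (adapted from the current manual) based on results from Aim 2", and "Standard REP will also include customized training based on Aim 2". Enhanced REP adds facilitators, and "Enhanced REP will also include additional training and packaging customization (e.g., supplemental ATOD resources").

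Table 3, in the Significance section, differs in part. It gives standard REP uncustomized training, and enhanced REP manuals tailored to each site. Table 7 lists "Identify core elements" as a pre-implementation activity, without linking it to the checklist.

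**The concern.** A fidelity score needs a fixed reference. Here the package is part of what is randomized, and the protocol does not say which version of the curriculum supplies the checklist items. Two problems could follow.

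- **Each arm or school is scored on its own package.** The set of items then depends on treatment, and the same teaching could give different scores.
- **All schools are scored on an older list.** A teacher who faithfully delivers a replaced component could be marked as not having delivered it.

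Either effect would be systematic, so more teachers would not remove it. It would fall on the first result that Aim 3a expects, higher adherence under enhanced REP. The ATOD outcomes and their model would not be affected.

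**Working it through.** The protocol gives no number of items, scoring rule or adherence figure, so there is nothing to reproduce. The check has two parts: what the text supports, and how far a distortion depends on assumptions.

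**1. What the text supports**

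Own-package scoring distorts the comparison only if (a) enhanced customization changes lesson components and (b) each arm or school is scored on its own list.

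- *Condition (a).* The only example of enhanced packaging in Aim 3, Procedures is extra resources on substance use, which need not alter any lesson component. Site-tailored manuals appear only in Table 3, a general description of REP adapted from an outside source. That tailoring draws on an organizational needs assessment, and Procedures describes no such assessment school by school.
- *Condition (b).* No sentence says so. The items are components of MMH lessons, and the expected gain is in adherence to the MMH curriculum, not to a school's package. Aim 3a labels adherence as a measure of MMH, and labels acceptability, appropriateness and feasibility as measures of REP. The Mid-Year Progress paragraph for Aim 3 speaks of one tailored curriculum and, separately, of a guide for deploying Enhanced REP. Table 7 has one line for adapting the manual and one for disseminating the package.

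The common-list problem also needs condition (a), in the form of components replaced for enhanced schools, together with a list that leaves out the replacements.

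**2. Arithmetic under assumptions**

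Assume a base list of 100 components with 60 taught in both arms. Standard score: 60/100 = 60.0%.

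*One common list, components unchanged:* the enhanced score is also 60/100, so the difference is 0.

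*Own list of length L for enhanced REP:*

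| L | Changed items all untaught: 60/L | Difference from 60% | Changed items taught at 60%: 0.6L/L | Difference |
|---|---|---|---|---|
| 80 | 75.0% | +15.0 | 48/80 = 60.0% | 0 |
| 90 | 66.7% | +6.7 | 54/90 = 60.0% | 0 |
| 110 | 54.5% | -5.5 | 66/110 = 60.0% | 0 |
| 120 | 50.0% | -10.0 | 72/120 = 60.0% | 0 |

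The nonzero differences require that every dropped or added item is untaught and that the score is a proportion. Under the same untaught assumption, a raw count is 60 in both arms, a difference of 0. The one adherence score that the protocol spells out, in Aim 1a, is a count of sessions and contacts. A count is not safe in general: with changed items taught at 60%, it would be 48 to 72 against 60. Only a common list removes the dependence on list length whatever the scoring rule.

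*Older common list, share s of taught components replaced:* the score is 60 × (1 - s). For s = 0.1 it is 54 (-6 points), and for s = 0.2 it is 48 (-12 points). This is not the same teaching scored differently, because the teacher delivered a replacement. It should not be pooled with the own-list figures.

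The result can be positive, zero or negative, depending entirely on inputs that the protocol does not supply.

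**The case for a change.** The strongest case for a change is that several versions of MMH will exist. The standard manual is itself adapted from the current one, and enhanced REP goes further. The single enhanced example is only an example, and the table cited for the arms allows manuals that differ by site. Referring to the curriculum does not choose among these versions, and the planned core-elements work is not tied to the checklist. A pilot meant to estimate effects and their direction should not leave the reference of a between-arm measure open, and naming it would cost almost nothing.

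Three parts of this stand. The version, the sharing of the list and the scoring rule are not stated. Table 3 and the Procedures text do not fully match on training and customization. An own-package list could distort the comparison. What does not stand is the step from silence to bias: packages that differ produce no scoring artifact unless the components differ and the list follows them, or the list leaves out replaced components. The Table 3 mismatch concerns how the arms are described, and which costs in Table 7 are shared. It does not determine how adherence is scored.

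**Conclusion.** No change to the plan follows. The protocol leaves out a measurement detail, but no stated rule gives a wrong adherence result. The natural reading is one list of MMH components for both arms, and under it identical teaching gives a difference of 0. The differences of +15.0 to -10.0 points (own list) and -6 to -12 points (replaced components) rest on an assumed list length, delivery rate and scoring rule, and cannot be taken as estimates for this study.

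The checklist is still to be created, so its items and scoring will be settled when it is written, and the core-elements activity in Table 7 gives the team an obvious basis. The stakes are limited: this is a pilot in eight schools whose stated overall purpose is appropriateness, feasibility and acceptability, and no sample size or power figure rests on adherence. The difference between Table 3 and the Procedures text is a matter of wording.

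This conclusion assumes that the team uses a common list reflecting the adapted curriculum. It would need revisiting if the finished instrument were scored separately by arm or school, or on a list that omits components replaced for enhanced schools.
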